#### 2.5.2 Secondary outcomes

There will be a number of secondary outcomes:

[figure not shown]
- The rate of IMG-related errors of any severity in each group
- The rate of moderate-severe non-IMG-related errors. This outcome will be measured because it is hypothesised that a more easily understood IMG monograph will enable participants to concentrate more on other aspects of the injection preparation and administration process.
- The rate of non-IMG-related errors of any severity in each group
- The mean time taken to prepare and administer the dose for each group. For each participant, the time will be measured from the point at which they start to read the simulated medication order or IMG monograph until the point at which they inform the observer that they would leave the simulated patient's bedside with the infusion running. This outcome will be measured

because it is hypothesised that a more easily understood IMG monograph will be read and interpreted more quickly, thus reducing the time required to prepare and administer the dose.

- The mean modified Decision Conflict Score (mDCS) for each group. This will be calculated from participant's responses to a modified Provider Decision Process Assessment Instrument (mPDPAI) immediately after they have finished preparing and administering the intravenous infusion. The mDCS is a measure of participants' degree of knowledge and uncertainty whilst making decisions during the preparation and administration of the medicine. It will be measured because it is hypothesised that a more easily understood IMG will result in participants having great confidence in the decisions made during the dose preparation and administration process.
- The mean monograph preference score of each group. Immediately after completing the mPDPAI, each participant will be shown the version of the IMG monograph they did not use to prepare the dose of medicine and asked to rate their preferred version using a seven point Likert scale. This will be measured because it is hypothesised that participants will prefer the more easily used IMG.

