Participant responses to the monograph preference question (question 23 in data collection tool) will be transformed into an ordinal scale ranging from 1 ("I strongly prefer guide X") to 7 ("I strongly prefer guide Y"). Subject to the distribution of the data, they will be summarised as the mean of all participants' responses and its 95% confidence interval to test the null hypothesis of no preference (mean = 4) at the 5% significance level. To investigate the possible influence of the monograph used for the simulation and hospital site on these data, the difference in mean between the two groups (and 95% confidence interval) will be calculated for each hospital and the overall data. These data will be modelled (logistic regression or Poisson regression, depending on the distribution), with the model incorporating hospital site as a random effect and the other characteristics as fixed effects.

As all data will be collected in a single session under the supervision of the Chief Investigator, full protocol adherence and complete data collection are likely to be achieved for all participants. However, should protocol non-adherence lead to a participant using the IMG version they were not allocated, data will be analysed on an as randomised (i.e. intention-to-treat) basis. Should this occur in more than 5% of participants, a per protocol analysis will also be presented for each outcome. Missing data will be ignored during the analysis, as this is likely to be minimal.

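### Poisson regression, one of two models named for the 1–7 preference score, is unsuitable: its standard errors ignore the observed spread and its result changes if guides X and Y are swapped

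*Protocol*

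**What the plan says.** Protocol section 2.5.2 lists preference among the secondary outcomes: "The mean monograph preference score of each group". After the simulation each participant sees both guides and is "asked to rate their preferred version using a seven point Likert scale".

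Section 4.3 (Statistical analysis of observation data) then gives three analyses of this score.

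- **Overall preference.** The mean of all responses and its 95% confidence interval are used "to test the null hypothesis of no preference (mean = 4) at the 5% significance level".
- **Influence of the guide used and of the site.** Here "the difference in mean between the two groups (and 95% confidence interval) will be calculated for each hospital and the overall data".
- **Adjusted model.** The wording is "These data will be modelled (logistic regression or Poisson regression, depending on the distribution". Site enters this model as a random term, and the remaining participant characteristics are fixed terms.

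The same section describes the score itself: "Participant responses to the monograph preference question (question 23 in data collection tool) will be transformed into an ordinal scale", with guide X at 1 and guide Y at 7. For the mDCS, which is also a bounded rating score (8 to 40), it plans linear regression, subject to the distribution.

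**The concern.** Poisson regression is a model for counts. A single rating on seven ordered categories is not a count, and two difficulties follow.

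1. **Standard errors.** Poisson takes the variance to be equal to the mean, so the standard error follows the average score and not the observed spread. Intervals are too wide when answers cluster in the middle or at the high end, and too narrow when answers are polarised.
2. **Direction of the scale.** Which guide is called X is a labelling choice. The log link and the variance rule are not symmetric under the change from score to 8 − score, so identical answers can give a different ratio, interval and p-value.

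At stake is the adjusted estimate of how far the guide used, the hospital and the other participant characteristics influence preference. Because the Protocol itself names the model, this is a model choice fixed badly, not a detail left to a later analysis plan.

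**Working it through.** **Inputs from the Protocol.** Score 1–7 (section 4.3); 121 to 172 participants per group (section 2.7); 1:1 allocation (section 1.5); 5% level. The Protocol states no figure for the preference model. The 121 itself reproduces for the primary outcome: 30% against 15%, two-sided 5%, 80% power, pooled variance and no continuity correction give 121 per group, with power 80.2%. It serves here only to fix the group size.

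**Inputs assumed.** The distribution of answers is not given, so several shapes are tried. Every calculation is a plain two-group comparison, without covariates or site effect.

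**Step 1: standard error and type I error.** With true mean m and variance v, the Poisson standard error divided by the true one is √(m/v). The actual type I error at nominal 5% is then about 2 × [1 − Φ(1.96 × √(m/v))]. For answers bell-shaped around 4, √(4.00/2.10) = 1.38, which gives 0.7%. The last column is from 20,000 simulated trials per shape.

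| Assumed answers | Mean | Variance | Poisson SE ÷ true SE | Type I, formula | Type I, simulated, 121 per group |
|---|---|---|---|---|---|
| Strongly towards Y | 6.03 | 1.89 | 1.79 | 0.05% | 0.06% |
| Skewed to Y | 5.37 | 2.51 | 1.46 | 0.4% | 0.4% |
| Bell-shaped around 4 | 4.00 | 2.10 | 1.38 | 0.7% | 0.8% |
| Skewed to X | 2.63 | 2.51 | 1.02 | 4.5% | 4.4% |
| Uniform | 4.00 | 4.00 | 1.00 | 5.0% | 5.2% |
| U-shaped | 4.00 | 6.48 | 0.79 | 12.4% | 11.9% |
| Half at 1, half at 7 | 4.00 | 9.00 | 0.67 | 19.1% | 18.4% |

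The rows skewed to Y and to X are mirror images with the same variance, so they are the same answers under the two labellings. Type I error is 0.4% under one and 4.4% under the other. Results at 172 per group are similar.

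**Step 2: one data set, two labellings.** Take group means 5.37 and 4.77, variances 2.51 and 3.10, 121 per group. The Poisson statistic is z = ln(m₁/m₂) ÷ √(1/(n·m₁) + 1/(n·m₂)).

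- As coded: ln(5.37/4.77) = 0.1185; SE = √(1/649.8 + 1/577.2) = 0.0572; z = 2.07, p = 0.038; ratio 1.13 (95% CI 1.01–1.26).
- Labels swapped, means 2.63 and 3.23: ln(2.63/3.23) = −0.2055; SE = √(1/318.2 + 1/390.8) = 0.0755; z = −2.72, p = 0.0065; ratio 0.81 (0.70–0.94). Its inverse is 1.23, not 1.13.
- Difference in means: 0.60 ÷ √((2.51 + 3.10)/121) = 2.79 in absolute value under either labelling.

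Simulated power in this example is 55% for Poisson as coded, 78% with labels swapped and 78% for the difference in means. A proportional-odds model gives about 82% (200 runs), and its |z| differs between labellings by at most 0.0005.

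**Step 3: a second skewed example.** Scores are normal with SD 1.6, rounded and limited to 1–7; 121 per group.

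- No difference between groups (resulting mean 5.36, SD 1.39): Poisson type I error 0.1% as coded and 2.5% swapped; t-test 5.4%.
- Underlying means 5.7 and 5.0: Poisson power 54% as coded and 83% swapped; t-test about 90%. At 172 per group the Poisson figures are 76% and 94%.

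**The case against.** The strongest reply is about reach, and most of it stands.

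- **The main preference results do not use Poisson.** A reader might infer that the trial's conclusion on preference depends on a label. It does not. The test of the mean against 4 and the between-group difference in means keep their p-values and interval widths when X and Y are swapped; only the direction reverses.
- **Poisson is conditional.** It is one of two options and may never be used. That is true, but no distribution of a bounded ordinal score makes a count model the natural choice.
- **Logistic may already mean ordinal.** A reader might infer a dichotomised score, with an unstated cut-point and lost levels. The Protocol's other logistic models are for binary outcomes, but here the outcome has just been called ordinal and no cut-point is given. The text does not establish the binary reading, so that criticism is not made.
- **The error is not always present or in one direction.** Poisson is about right for uniform answers or answers skewed to X. Where answers cluster towards Y the test is conservative and the cost is power. The inflated error needs polarised answers, which nothing in the Protocol predicts.
- **The planned model has site and covariates.** The figures come from a simpler comparison and are illustrative.
- **A variance correction could be added.** Quasi-Poisson or robust standard errors would repair the variance, but the ratio would still depend on the label.

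What remains is that the Protocol names a model that does not match the outcome it has just defined.

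**Conclusion.** The point holds in a limited form. Poisson regression is unsuitable for this score, and its result depends on which guide is labelled X. Under the assumed shapes, at 121 per group and without covariates or site effect, type I error runs from about 0.1% through 5% to 12–19%. In one skewed example power is 54% or 83% according to the label, against about 90% for a t-test. None of these percentages predicts what this trial would see, because the distribution of answers is unknown.

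The consequence is confined to the adjusted model of one secondary outcome. Nothing here reaches the primary outcome, and nothing here argues against the stated random effect for hospital site. It is a minor but worthwhile correction.

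**What to change.** In section 4.3, delete Poisson regression for the preference score and state that the model is a proportional-odds (ordinal logistic) regression. Reversing the scale then changes only the sign of the effect, not the test. A linear model, as planned for the mDCS, with robust standard errors if needed, would also serve. Keep hospital site and the other characteristics in the model as now stated.

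The cost is one sentence. No extra data are needed, and section 4.3 already names STATA and R, which fit these models. The choice should be written down before the preference data are examined, so that it does not depend on the result.

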### Debrief interview data analysis

A basic content analysis will be performed to quantify the proportion of errors where the participant stated that:

- i. the error was related to the IMG monograph, or
- ii. the error could have been prevented by a change to the monograph.

Transcripts will be independently coded for the presence or absence of the above two statements by two independent coders. Disagreements between the two coders will be resolved by discussion until consensus is achieved.

In addition, the transcript of each interview will also be subject to thematic analysis with a focus on describing the causes of the observed errors using the Yorkshire contributory factors framework. Thematic analysis is an approach which allows the identification of recurrent themes and the exploration of their meaning and will be applied by following the six stages described by Braun and Clarke. Nvivo software will be used during this process.

## 5 ETHICS AND DISSEMINATION

#### 5.1 Research ethics approval and other regulatory review

As participants in this study are NHS staff, review by an NHS Research Ethics Committee is not required. However, a favourable opinion will be sought from the University of Bath Research Ethics Approval Committee for Health (REACH) for this protocol, informed consent forms and other relevant documents.

Approval from the Health Research Authority (HRA) will be obtained before the study commences. Before the study commences at a particular site, the Chief Investigator will ensure that the R&D department of that site has formally confirmed their capacity and capability to deliver the study.

Should any study amendments be required, the Chief Investigator will submit information to REACH and the HRA in order to seek their approval for each amendment. The Chief Investigator will then work with study sites' R&D departments so they can put the necessary arrangements in place to implement the amendment and to confirm their support for the study as amended.

## 5.2 Amendments

Amendments will be submitted for approval and communicated as described above. The decision to make amendments will be made and implemented by the Chief Investigator, in line with advice from the Study Advisory Group and research advisors. The sponsor will categorise amendments as substantial or non-substantial in line with their guidelines applicable at the time. Amendment history will be tracked through the use of version numbers of all documents and Appendix 2 of this protocol.

## 5.3 Consent

Informed consent will be obtained from all participants and recorded in writing immediately prior to their *in situ* simulation. Data collection will not commence unless consent is obtained and documented.

The Chief Investigator will work with study sites to circulate information about the study to all wards where *in situ* simulation is planned. Suitable simulation times will be agreed in advance with ward managers, who will circulate paper or electronic copies of the participant information leaflet and consent form to all nurses who will be on duty at this time at least 24 hours in advance of the simulation.

Immediately prior to a participant's simulation session, the Chief Investigator will discuss the contents of the participant information leaflet with the participant, highlighting the nature and objectives of the study and possible risks associated with participation. The participant will be given the opportunity to ask questions about any aspect of the study they do not fully understand. As participants in this study will be qualified, practising nurses, it is very likely that all potential participants will have capacity to consent. If the potential participant demonstrates the ability to retain and understand the information provided about the study, they will be deemed capable and asked to complete the consent form.

## 5.4 Confidentiality

All investigators must comply with the requirements of the University of Bath Research Data Policy, which is based on current national data protection requirements.

Personal information will be collected via consent forms and demographic data collection. However, demographic data will be collected anonymously. Paper forms will be returned to the University of Bath as soon as possible after completion, where they will be stored in a locked cabinet in a locked office.

The debrief interview audio recordings can also be considered personal information. They will be made using a password protected digital recorder and then transferred to the University of Bath's secure managed data storage facility as soon as a suitable secure network connection is available. They will be deleted from the digital recorder at this point. Recordings will subsequently be transcribed. Transcriptions will also be stored in a password protected folder in the University of Bath's secure managed data storage facility and will be anonymised by replacing any potentially identifiable information with an unrelated sequence of characters.

Participants will not be identifiable from the video recordings made to investigate observer reliability, as only their hands will be recorded. However, video files will be transferred to the University of Bath's secure managed data storage facility as soon as a suitable secure network connection is available and then deleted from the digital recorder.

All data will be identified using only a unique participant number. Records linking unique participant numbers with identifiable individuals will not be made.

Data will be shared with team members outside the University of Bath using the secure files.bath file sharing facility (www.bath.ac.uk/guides/access-and-share-your-work-online-using-files-bath/). Data will

be stored for ten years, in accordance with the University of Bath Research Data Policy (www.bath.ac.uk/research/data/policy/).

## 5.5 Declaration of Interests

The Chief Investigator has no financial or other competing interests to declare.

## 5.6 Access to data

Access to data will be limited to the Chief Investigator, research advisors and sponsor's representatives. Suitable anonymised data may be made available via the University of Bath Research Data Archive (https://researchdata.bath.ac.uk/).

## 5.7 Dissemination policy

Data arising from this study will be owned by the University of Bath. On completion of the study, data will be analysed and tabulated and a Final Study Report submitted to the NIHR. This report will be accessible via the NIHR. The Chief Investigator will have the right to publish any of the study data, subject to acknowledgement and approval of the submission by the NIHR.

Participants who on their consent form express an interest in finding out about the results of the study will be sent a copy of the final study report.

The study protocol, final study report and anonymised participant level dataset may be made publicly available via the University of Bath Research Data Archive (https://researchdata.bath.ac.uk/) at the conclusion of the study.

The author of the final study report will be the Chief Investigator. Authorship of academic publications arising from this study will be determined according to the International Committee of Medical Journal Editors criteria for defining the role of authors and contributors:

- Substantial contributions to the conception or design of the work; or the acquisition, analysis, or interpretation of data for the work; AND
- Drafting the work or revising it critically for important intellectual content; AND
- Final approval of the version to be published; AND
- Agreement to be accountable for all aspects of the work in ensuring that questions related to the accuracy or integrity of any part of the work are appropriately investigated and resolved.

See: www.icmje.org/recommendations/browse/roles-and-responsibilities/defining-the-role-of-authors-and-contributors.html

## 7. APPENDICIES

#### 11.1 Appendix 1 – Required documentation

- CV of Chief Investigator
- Participant information sheet
- Consent form
- Microsoft Excel data collection tool
- Structured observation schedule
- Debrief interview schedule

Amendment No.	Protocol version no.	Date issued	Author(s) of changes	Details of changes made
1	1.1	31/1/2019	[name]	Excel data collection tool for demographics and participant feedback data changed to paper form
2	1.2	5/6/2019	[name]	Secondary outcomes description amended to make it clear that these will consider the rates of errors of all severity, not just minor errors (not a protocol change, but a clarification). Given the high prevalence of errors found in the project so far and difficulty finding suitable private space, debrief interview procedure amended to specify that only participants making IMG-

## 13.3 Appendix 2 – Amendment History

related errors will be invited to take part in an interview, and this will only take place if a suitable private space is available and the participant does not have urgent clinical tasks to carry out.
Severity panel procedure amended to remove the validation that the observation was indeed an error, as this role is better fulfilled by the video analysis. Panel voucher payment increased to £50.
